**Open Label Study of Subcutaneous Immunoglobulin (SCIg)
in Myasthenia Gravis**

NCT02100969

February 22, 2019

Data Analysis Plan and Statistical Considerations:

1. Analysis of Primary Outcome:

At the end of the 9-week IVIg screening phase, baseline QMG scores of all the patients will be recorded. At the end of SCIg experimental treatment phase (Week 12), the QMG score will be captured and compared to Week 0. If the increase in QMG scores from Week 0 to Week 12 in the experimental treatment phase is found to be no more than 3 points, then they will be considered to be a 'success' in terms of their response. We hypothesize that the positive response rate of these patients is at least 70%. Allowing a margin of 5%, our hypotheses are formally stated below:

Null hypothesis H_0 : Proportion of patients whose QMG scores are increased by more than 3 points at the end of the SCIg treatment phase ≤ 0.65

Alternate hypothesis H_A : Proportion of patients whose QMG scores are increased by no more than 3 points at the end of the SCIg treatment phase > 0.65

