This hypothesis will be tested using a one sided one sample test of proportions with the normal approximation, at the 5% significance level. We will also report a 95% confidence interval for the true proportion of subjects who experience a 'success' as with a sample size of 25 patients, we will have a margin of error of 0.19. In the experimental treatment phase, patients who either experience treatment failure (as previously defined on pg. 22) or clinical deterioration (as defined above on pg. 22) will be withdrawn before Week 12 and we will therefore impute for both non-positive responses at Week 12, a discrete QMG score increase of more than 3 points. For example, if the largest deterioration score observed is 8, then a QMG score ranging between 4 and 8 will be imputed at Week 12. Although we do not expect many missing observations at Week 12 of the SCIg phase, the outcomes recorded at these intermediate time points will allow us the ability to impute data at this endpoint. Specifically, in the case where no outcome is available for a subject at Week 12 due to the subject's perception of a worsened condition, we will impute for this subject a QMG score increase at Week 12 of more than 3 points. In cases where subjects refuse to proceed to Week 12 or are lost to follow-up even though they were responding well on the treatment (as evidenced by the intermediate measurements), we will impute their Week 12 observation using the last observation carried forward (LOCF) approach. We will complement our LOCF approach with sensitivity analyses covering the following alternate approaches: (1) Multiple imputation with 5 replicates per imputation to account for the uncertainty inherent to the imputation (2) Mixed model calculations accounting for the trend in QMG values over time (3) Best case and worst-case scenarios.

2. Additional Exploratory Analysis of Primary Outcomes:

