
4. Sample Size Considerations:

With a sample size of 25 patients, we have at least 70% power to detect a success rate of 85% or higher using the chi-square test compared to an expected success rate of 65% or lower. We anticipate we will be able to assess efficacy, safety and tolerability of SCIg with the current sample size over 12 weeks and compare that these parameters to the 12-week IVIg phase. The selected sample size will enable us to complete study enrollment with the current number of sites.

MG is a rare disease and MG studies have consistently experienced difficulty enrolling subjects due to a multiplicity of poorly understood reasons.³⁴ In the Methotrexate study of MG and similar to other previous MG studies, enrollment has been a challenge. However, we managed to complete enrollment of 50 subjects by adding sites. In the current SCIg study protocol, the eligible

study population is narrowed due to the inclusion criterion requiring MG cases to be on stable IVIg doses. While 85 to 90% of MG patients are seropositive for either the AchR or MuSK autoantibodies, some of these cases are treated in clinical practice with IVIg maintenance. Based on the pre-site selection feasibility survey, 25 subjects is a reasonable and achievable goal with the selected five sites. If enrollment is found to be slower than predicted, we are ready to add more sites to complete this study.

5. Study Populations:

Safety population: All patients enrolled at baseline constitute the safety population. The subjects in this population will be included in the analysis of adverse events, vital signs, clinical laboratory findings, and other safety data. But for the purpose of statistical analyses, the rates of adverse events experienced by these subjects in the SCIg phase will be compared to the rates experienced during the IVIg phase of the study. Adverse events will be tabulated by treatment group, severity, and perceived relationship to study drug. For each adverse event, the treatment groups will be compared regarding the occurrence of at least one event using the Fisher's exact test. The comparisons will be repeated excluding all mild symptoms. Continuous measures such as vital signs and laboratory test results will be analyzed in a manner similar to that for the primary outcome variable.

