Intent to treat population (ITT): Only those patients who receive at least one dose of SCIg are considered to be the primary population which is the same as ITT population. The ITT will be included in the analysis of baseline findings and efficacy results. Only those patients who receive at least one dose of SCIg are considered to be the primary population and the intent-to-treat population.

Unscheduled visits: In the event that there are unscheduled patient visits, we will report the frequency of such visits for the two phases of the study. We will also document the date and reason for such visits and assess if these visits are systematic or random. If occurrence of such visits is due to side effects we will compare the rates of such events across the two phases of the study. Testing at unscheduled visits is done only to check and assess clinical worsening. If no worsening is found, patients will continue to be a part of the study. If a patient experiences a worsening event that does not qualify as clinical deterioration (per pg. 22) and the investigator determines it is safe for that patient to continue, the patient will remain in the study. On the other hand, if a patient experiences a worsening event that qualifies as clinical deterioration the patient will be withdrawn from the study. We will compare the within-person variation to the cross-person variation for the overall data. If the within-person variation is found to be less than the cross-person variation, we will use a LOCF approach to impute the patient's QMG score at the next time point and do a sign rank test on that time point and baseline. On the other hand, if the within-person variation is found to be greater than the cross-person variation, we will impute the observation at the next time point followed by a sign rank test.

SAS 9.4 will be used for all analyses. All data management and statistical analysis will be performed in the Department of Biostatistics at the University of Kansas Medical Center. The Velos Clinical Research Information System (CRIS) will be used at all sites to enter and view data. This will be available to the safety monitors (see below).

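### The primary z test can exceed its stated 5% because its form is not fixed and the number tested need not be 25, and the printed H_0 is not the complement of H_A

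*SAP*

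**What the plan says.** A success is a QMG rise of at most 3 points from Week 0 to Week 12. Section 1 (Analysis of Primary Outcome) hypothesises a response rate of at least 70%, takes off a 5-point margin, and prints two hypotheses:

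- H_0: "Proportion of patients whose QMG scores are increased by more than 3 points at the end of the SCIg treatment phase ≤ 0.65"
- H_A: "Proportion of patients whose QMG scores are increased by no more than 3 points at the end of the SCIg treatment phase > 0.65"

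It then names the test: "This hypothesis will be tested using a one sided one sample test of proportions with the normal approximation, at the 5% significance level". It does not say whether the standard error uses the null value or the observed proportion, or whether a continuity correction applies.

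Section 4 (Sample Size Considerations) states: "With a sample size of 25 patients, we have at least 70% power to detect a success rate of 85% or higher", and continues: "using the chi-square test compared to an expected success rate of 65% or lower". It gives neither sidedness nor significance level, and it discusses 25 as an enrolment goal.

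Section 5 (Study Populations) fixes the denominator by dosing: "Only those patients who receive at least one dose of SCIg are considered to be the primary population and the intent-to-treat population".

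**The concern.** Three things leave the primary test loosely fixed.

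1. **Hypotheses.** H_0 as printed bounds the proportion who worsen, while H_A concerns the proportion who do not. They should divide the same parameter at 0.65.
2. **Form of the test.** With about 25 binary outcomes, an uncorrected normal approximation can run above or below its nominal level. Which way it goes depends on the exact number tested and on the variance form, and the SAP fixes neither.
3. **Section 4.** It names a chi-square test where Section 1 names a one-sample test of proportions, and it calls the null value an expected rate.

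At stake is the false-positive rate of the primary claim. In some plausible samples, a result could be declared significant at 5% when its exact one-sided p-value is above 5%. Two analysts following Section 1 could also reach different conclusions from 20 successes in 25.

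**Working it through.** **Inputs.** Null success rate 0.65 (H_A in Section 1; Section 4). Design alternative 0.85, n = 25 and power of at least 70% (Section 4). One-sided 5%, critical value 1.645 (Section 1). The number tested is the number dosed with SCIg (Section 5). The SAP gives no such number, so 22 to 26 is an assumed range.

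**1. The SAP's power figure.** By the normal formula, power = Φ[(0.85 − 0.65 − 1.645·SE0)/SE1].

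- SE0 = √(0.65×0.35/25) = 0.0954
- SE1 = √(0.85×0.15/25) = 0.0714
- Power = Φ[(0.20 − 0.1569)/0.0714] = Φ(0.603) = 72.7%

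The statement of at least 70% therefore reproduces. A two-sided 5% version (1.960) gives 57.2%, so Section 4 was evidently computed one-sided.

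**2. The printed hypotheses.** Let p be the success proportion, so the proportion worsening by more than 3 points is 1 − p. H_0 as printed says 1 − p ≤ 0.65, that is p ≥ 0.35. H_A says p > 0.65. At p = 0.80 both are true; at p = 0.30 neither is. The steps below use the evident intent, p ≤ 0.65.

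**3. Size of the null-variance z test, no continuity correction.** z = (x/n − 0.65)/√(0.65×0.35/n), rejecting when z > 1.645. True size is P(X ≥ cut-off | n, 0.65), which is also the exact one-sided p-value at the cut-off. At n = 25, 20 successes give z = 1.572 and 21 give z = 1.992, so the cut-off is 21.

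| n | z-test cut-off | z | z-test p | True size | Power at 0.85 |
|---|---|---|---|---|---|
| 22 | 18 | 1.654 | 0.049 | 0.0716 | 0.7738 |
| 23 | 19 | 1.771 | 0.038 | 0.0551 | 0.7440 |
| 24 | 20 | 1.883 | 0.030 | 0.0422 | 0.7134 |
| 25 | 21 | 1.992 | 0.023 | 0.0320 | 0.6821 |
| 26 | 21 | 1.686 | 0.046 | 0.0649 | 0.8150 |

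**4. Other forms that the wording allows.**

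- *Sample variance:* 20 of 25 gives z = (0.80 − 0.65)/√(0.80×0.20/25) = 0.15/0.08 = 1.875, so the test rejects at 20. Size is then 0.0826 and power at 0.85 is 0.8385. Sizes at 22, 23, 24 and 26 are 0.0716, 0.0551, 0.1044 and 0.0649.
- *Null variance with continuity correction:* cut-offs at 22 to 26 are 19, 20, 20, 21 and 22. Size is at most 0.0422 throughout.

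**5. Exact one-sided binomial test at 5%.**

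| n | Cut-off | Size | Power at 0.85 |
|---|---|---|---|
| 22 | 19 | 0.0245 | 0.5752 |
| 23 | 20 | 0.0181 | 0.5396 |
| 24 | 20 | 0.0422 | 0.7134 |
| 25 | 21 | 0.0320 | 0.6821 |
| 26 | 22 | 0.0242 | 0.6505 |

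At 24 and 25 the cut-off equals that of the null-variance z test. At 22, 23 and 26 it is one success higher.

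**The case against.** **Power.** A reader might infer that Section 4's power claim is an arithmetic error, because the exact power of the 21-of-25 rule is 68.2%. The documents do not support that. Section 1 declares a normal approximation, and that approximation gives 72.7%. The exact value is 1.8 points below 70%, the gap comes from discreteness, and the 68.2% itself assumes the null-variance form. This part of the objection stands in full.

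**Chi-square.** A reader might also infer that Sections 1 and 4 name different tests. A one-sample chi-square statistic is the square of the null-variance z, so a one-sided chi-square is the same test. Read as two-sided, it shifts the cut-off by one success at 22, 23, 24 and 26, and not at 25. This is a labelling matter.

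**Size.** At 25, the only sample size in the SAP, the null-variance test has size 3.2%. Section 4 regards 25 as achievable and allows sites to be added, and at 23 the excess over 5% is only half a point. A continuity correction would remove the excess altogether. All of this is fair, and it rules out saying that the planned test breaches 5% as such. It does not remove the point: the SAP specifies no correction and no variance form, and its denominator is set by dosing.

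**Cost of an exact test.** It lowers power at 22, 23 and 26, and accepting an approximate test in a small open-label rare-disease study could be defended. But the z test's extra power at those sizes comes from exceeding the level that the SAP states.

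**Intent of H_0.** The printed H_0 is unlikely to mislead the analysis, since H_A, the 70% less 5% reasoning and Section 4 all point to a success rate of 0.65. It is still wrong as printed.

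**Conclusion.** The point holds in a limited form. H_0 as printed is not the complement of H_A and needs rewording. Separately, the primary test as specified does not reliably hold its stated 5%. In the null-variance form without continuity correction, it is within 5% at 24 and 25 treated patients (4.2%, 3.2%) and above it at 22, 23 and 26 (7.2%, 5.5%, 6.5%). In the sample-variance form it is above 5% even at the planned 25 (8.3%).

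These figures assume a null of success ≤ 0.65 and the range of 22 to 26 treated, which is not the SAP's. With a continuity correction the excess disappears, so the weakness is that the test is under-specified rather than wrong in every form. The power statement in Section 4 is consistent with the SAP's own method.

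**What to change.** 1. **Section 1, H_0.** Reword it as: the proportion of patients whose QMG rises by no more than 3 points from Week 0 to Week 12 is ≤ 0.65.
2. **Section 1, test.** Replace the normal-approximation test with the exact one-sided binomial test at 5% against 0.65. State the cut-off as 21 or more of 25, recomputed for the number treated with SCIg: 19 of 22, 20 of 23, 20 of 24, 22 of 26.
3. **Section 4.** Name the same test in place of the chi-square test, state one-sided 5%, and call 65% the null success rate rather than the expected one. Once the exact test is named, give power as about 68% at a success rate of 85%.

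The cost is SAP wording, with no extra patients and no change to the rule at 25 under the null-variance reading. The stated power becomes slightly less favourable. If 22, 23 or 26 patients are treated, one more success is needed than under the null-variance z test, and power at 85% falls from 77.4% to 57.5%, from 74.4% to 54.0%, and from 81.5% to about 65%.

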Analysis of secondary outcome measures as listed in the Aims section such as MG-ADL, MG QOL-15, the MG composite score and TSQM will primarily be conducted only for those who complete the study. We will conduct a two-sided signed-rank test to assess whether these scores changed significantly from baseline (Week 0) to Week 12. In case of missing values for the MG-ADL, MG QOL-15, and the MG composite score in cases where subjects refuse to proceed to Week 12 even though they were responding well on the treatment (as evidenced by the intermediate measurements) or are lost to follow-up, we will impute their Week 12 observation using the last observation carried forward (LOCF) approach. We will also report the proportion of subjects enrolled in the subcutaneous experimental treatment study phase (Week 0 to Week 12) fulfilling our definition of improvement (as mentioned on pg. 24) along with a 95% confidence interval. We will compare between the two phases the percent of subjects meeting the definition of deterioration, worsening, stability and improvement. We will analyze the effect of prednisone dosage (Increase vs Not Increased) on clinical improvement (Yes vs No) using a 2x2 Fisher's exact test in the SCIg phase of the study by comparing dose levels at Week 12 to Week 0 for those patients who complete Week 12 of the study. To do this, we will ask the patients at Week 0, Week 4, Week 8 and Week 12 about their prednisone dosage levels. Those patients who exit the study prematurely due to deterioration before Week 12 will be excluded from this Fisher's test calculations. In the event that the Week 12 prednisone dose observation is missing even when patients have completed Week 12 (QMG or MGADL done), we will use the LOCF approach to impute this missing value as long as at the last available assessment, the patient was deemed to be improving (in terms of QMG or MGADL scores as defined under "Subject deterioration, worsening, rescue medication and improvement"). A two-sided signed-rank test will be also conducted to assess whether IgG levels changed significantly between the intravenous screening phase (Week -10 to Week 0) to the subcutaneous experimental treatment study phase (Week 1 to Week 12). All tests will be conducted at the 5% level of significance. For the secondary outcome measures related to monitoring the safety profile of patients between the two study phases, a similar test will be conducted when the safety parameters measured are continuous variables and a one sample test for the difference in proportions will be conducted when they are measured as treatment-related severity rates. The comparison epochs for safety are also between the intravenous screening phase (Week -10 to Week 0) and the subcutaneous experimental treatment study phase (Week 0 [after first SCIg dose] to Week 12). Adverse events occurring in the two phases (mild, moderate/severe) will be summarized using a McNemar's test.

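### Beyond tabulation, adverse events are compared between phases only by 5% significance tests, with no interval estimates, and 25 patients give those tests little ability to tell worse from similar

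*SAP*

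**What the plan says.** Section 4 of the SAP says "We anticipate we will be able to assess efficacy, safety and tolerability of SCIg with the current sample size over 12 weeks" and that these will be compared with the IVIg phase. The only power figure beside this statement concerns the efficacy response: "With a sample size of 25 patients, we have at least 70% power to detect a success rate of 85% or higher", "compared to an expected success rate of 65% or lower".

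For adverse events, Section 5 (Safety population) plans a tabulation by group, severity and relationship to study drug, and then testing: "For each adverse event, the treatment groups will be compared regarding the occurrence of at least one event using the Fisher's exact test". It continues: "The comparisons will be repeated excluding all mild symptoms". Section 3 adds "Adverse events occurring in the two phases (mild, moderate/severe) will be summarized using a McNemar's test", a one-sample test for the difference in proportions for treatment-related severity rates, and the rule "All tests will be conducted at the 5% level of significance".

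Ninety-five per cent intervals are planned in two places only: for the success proportion (Section 1, with a margin of error of 0.19) and for the proportion improved (Section 3).

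**The concern.** Section 4 presents safety and tolerability as something this sample size can address, including against the IVIg phase. The inference that follows is a set of p-values. In a small study a p-value above 0.05 does not show whether the SCIg-phase rate is similar to the IVIg-phase rate or merely uncertain. An interval for the difference does show this, and the plan uses intervals where efficacy is at issue.

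At stake is how the safety results can be read. The tables may contain mostly non-significant per-event comparisons, some for events seen only on SCIg, with nothing to show how large an excess the data leave open. The primary efficacy result is not affected.

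**Working it through.** **Inputs from the SAP.** n = 25 (Section 4); 5% level (Section 3); Fisher's test per event (Section 5); McNemar's test by severity (Section 3).

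**Assumptions, because the SAP does not give them.** All 25 patients contribute to both phases; adverse-event tests are two-sided; IVIg-phase event rates run from 0 to 40%; the phases are independent within patient unless stated. The version of McNemar's test is not specified, so both exact and uncorrected forms are shown.

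**1. The plan's own power figure.** One-sided z test, 85% against 65%, n = 25:

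Power = Φ[(0.20 × √25 − 1.645 × √(0.65 × 0.35)) / √(0.85 × 0.15)] = Φ[(1.000 − 0.785) / 0.357] = Φ(0.603) = 72.7%.

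This agrees with the stated figure of at least 70%. No counterpart is given for safety.

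**2. Where the tests begin to reject: event in no IVIg-phase patient and k SCIg-phase patients.**
- Fisher, 25 per phase, k = 5: p = 2 × C(25,5)/C(50,5) = 2 × 53,130/2,118,760 = 0.0502.
- Fisher, k = 6: p = 2 × C(25,6)/C(50,6) = 2 × 177,100/15,890,700 = 0.022.
- Fisher, k = 5 with fewer patients per phase: 0.0471 (20), 0.0485 (22), 0.0491 (23), 0.0496 (24).
- Exact McNemar: p = 2 × 0.5^k, so 5:0 gives 0.0625 and 6:0 gives 0.031.
- Uncorrected McNemar: χ² = k on 1 df, so 4:0 gives 0.0455.

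**3. Probability of missing a 20-point rise.** For 0% rising to 20%, the number affected on SCIg is binomial(25, 0.20). Fisher and exact McNemar need at least 6: P(X ≥ 6) = 0.383, so 62% are missed. Uncorrected McNemar needs at least 4: P(X ≥ 4) = 0.766, so 23% are missed. The other rows sum the probabilities of all rejecting tables.

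| IVIg to SCIg rate | Fisher | Exact McNemar | Uncorrected McNemar |
|---|---|---|---|
| 0 to 20% | 62% | 62% | 23% |
| 5 to 25% | 63% | 68% | 50% |
| 10 to 30% | 70% | 72% | 61% |
| 20 to 40% | 77% | 78% | 70% |
| 30 to 50% | 77% | 80% | 73% |
| 40 to 60% | 76% | 80-81% | 73% |

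The result also depends on pairing. If every patient with the event on IVIg also has it on SCIg (full nesting), Fisher misses 68-89% for IVIg-phase rates of 5 to 30%, because it ignores the pairing. Under that pattern exact McNemar misses 62% and uncorrected McNemar 23%. The one-sample test was not calculated separately, since its form is not fixed.

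**4. What intervals would show.**
- Event seen in 0 of 25: upper bound 1 − 0.05^(1/25) = 11.3% (one-sided 95%), or 1 − 0.025^(1/25) = 13.7% (two-sided 95%).
- Event in 3 patients in each phase, one of them in both: difference 0, Newcombe paired 95% interval about −19 to +19 points.
- Event in 5 SCIg-phase patients and no IVIg-phase patient: difference +20 points. The Wilson limits are 8.9-39.1% for 5/25 and 0-13.3% for 0/25. Newcombe lower limit = 0.200 − √[(0.200 − 0.089)² + 0.133²] = 0.026; upper limit = 0.391. The interval of about +3 to +39 points tells the reader far more than p = 0.0502 does.

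**The case against.** The strongest reply is that the SAP states nothing false here. Events are tabulated side by side, so an imbalance of 5 against 0 would be visible whatever its p-value. Section 4 says only that the investigators expect to assess safety; it claims neither equivalence nor non-inferiority. The study is small because the disease is rare, and low per-event power follows from that.

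Much of this stands, and it rules out three stronger readings.
- A reader might infer that the safety comparison consists of p-values alone. It does not: the tabulation is planned, and Section 3 also tests by severity. What is missing is interval estimation.
- A reader might infer that the plan will take non-significance as evidence of safety. The SAP nowhere says so.
- A reader might infer that the tests can never flag an event in 5 SCIg-phase patients and none on IVIg. That holds for two-sided Fisher at exactly 25 per phase, where p = 0.0502 is borderline. At 20 to 24 per phase the value falls just below 0.05, and uncorrected McNemar already rejects at 4:0.

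Uncorrected McNemar's 23% miss rate when the IVIg-phase rate is zero is also no worse than the 30% that the plan's 70% power accepts for its primary outcome. That is the favourable end of its range, however; at IVIg-phase rates of 5% or more, with independent phases, it misses 50-73%. A table of counts also does not express the uncertainty in a difference.

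**Conclusion.** The point holds as a gap in method, not as an error of fact. The SAP commits to a between-phase safety comparison, limits its inference to 5% significance tests and plans no interval for adverse events, while giving intervals for efficacy proportions. With about 25 patients, most of the plausible tests miss most 20-point rises. The sizes rest on the assumed IVIg-phase rates, two-sided testing and independence between phases, and they vary with the version of McNemar's test. The missing intervals and the absence of any precision statement in Section 4 depend on none of these assumptions.

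A related inconsistency sits in the same sentence of Section 5: Fisher's test treats two phases of the same patients as independent groups, whereas Section 3 uses the paired McNemar test. Resolving that alone would leave the intervals still missing.

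**What to change.** **Section 5.** Keep the tabulation. For any adverse event, any moderate or severe event, and each event type, report the within-patient SCIg minus IVIg difference in the proportion with at least one event, with a paired 95% interval (for example Newcombe). Add the exact 95% upper bound on the SCIg-phase rate. Replace Fisher's test with a paired test consistent with Section 3, name its version and sidedness, and label per-event p-values descriptive. A score-type interval and an exact test can disagree at the margin, as in the 5 against 0 example (interval above zero, exact McNemar p = 0.0625), so state that the interval is the basis for interpretation.

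**Section 4.** State the attainable precision, for example that an event seen in none of 25 patients remains compatible with a true rate of up to 11.3% (one-sided 95%) or 13.7% (two-sided 95%).

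**Cost.** SAP wording and a few table columns; no new data, visits or patients. The tables become longer and the safety statement less favourable.

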Additional exploratory analysis will be carried out treating QMG scores at baseline, Week 4, Week 8 and Week 12, as a continuous response variable. Descriptive statistics will be reported using means and standard deviations if the distribution of QMG scores is found to be normal and using medians and interquartile range if they are found to be non-normal. One advantage of reporting scores at the intermediate weeks is that it will allow us to assess whether or not some patients on SCIg stabilize early in terms of the QMG scores. It will also allow us to study the trend over time in an exploratory manner. We will further complement our exploratory analysis by conducting a two-sided non-parametric signed rank test in order to assess whether the QMG scores changed significantly after switching from IVIg to SCIg. Also, we will dichotomize the QMG into two groups

(high and low) based on clinically relevant thresholds and compare the differences in proportions at end of study and baseline.

3. Analysis of Secondary Outcomes:

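### Section 5 applies Fisher's exact test, which needs independent groups, to adverse events in two phases of the same patients, while Section 3 names McNemar's test for those phases

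*SAP*

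**What the plan says.** The design is a single cohort. Section 2 tests "whether the QMG scores changed significantly after switching from IVIg to SCIg", and the SAP describes no parallel arm.

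Section 5 (Safety population) first sets a within-patient comparison: the adverse event rates "experienced by these subjects in the SCIg phase will be compared to the rates experienced during the IVIg phase". It then changes to the language of parallel groups. "Adverse events will be tabulated by treatment group, severity, and perceived relationship to study drug", and for each event "the treatment groups will be compared regarding the occurrence of at least one event using the Fisher's exact test". It adds: "The comparisons will be repeated excluding all mild symptoms".

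Section 3 fixes the safety epochs as the IVIg screening phase (Week -10 to Week 0) and the SCIg phase (Week 0, after the first SCIg dose, to Week 12). It then says: "Adverse events occurring in the two phases (mild, moderate/severe) will be summarized using a McNemar's test".

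The SAP does not say how the two rules relate or which governs where they overlap.

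**The concern.** The only treatment groups available are the two phases of the same people. Each patient supplies one yes/no answer on IVIg and one on SCIg. Fisher's exact test takes these as answers from different people and ignores the pairing, so its real error rate depends on the within-patient correlation.

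The two sections also prescribe different methods for closely related comparisons. The breakdowns are not identical: Section 3 works by severity class, Section 5 by individual event and then again without mild ones. That repeat comes close to Section 3's moderate/severe class, so there is real overlap.

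At stake is whether an increase in an adverse event after the switch is declared significant, and whether that depends on the section the analyst follows. The primary outcome is not touched.

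**Working it through.** The SAP gives no figure for this comparison, so there is none to reproduce. The check measures what the choice of test does.

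**Inputs.** From the SAP: 25 patients (Section 4) and a 5% level (Section 3). Assumed: two-sided testing (sidedness is not stated for these tests), all 25 patients observed in both phases, the event rates, and the within-patient correlation phi.

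**Why pairing matters.** With the same event probability p in both phases and n patients, the difference in observed proportions has variance 2p(1-p)(1-phi)/n. Independent groups would give 2p(1-p)/n. At phi = 0.5 the true variance is half of what Fisher's test presumes; at phi = -0.5 it is 1.5 times as large.

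**Enumeration.** Joint probabilities for IVIg rate p1 and SCIg rate p2:

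- both phases: p11 = p1·p2 + phi·√[p1(1-p1)p2(1-p2)]
- IVIg only: p1 - p11
- SCIg only: p2 - p11
- neither: the remainder

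Every possible table of 25 pairs was weighted by its multinomial probability. Fisher's test was applied as if there were two groups of 25. Exact McNemar was applied to the discordant pairs b and c: p = 2·P(X ≤ min(b,c)), capped at 1, with X binomial(b+c, ½). Rejection means p ≤ 0.05.

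**Error rate with no true difference, 40% vs 40%**

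| phi | Fisher | Exact McNemar |
|---|---|---|
| -0.5 | 0.076 | 0.031 |
| -0.3 | 0.057 | 0.029 |
| 0 | 0.030 | 0.024 |
| 0.3 | 0.009 | 0.020 |
| 0.5 | 0.002 | 0.013 |

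At 30% vs 30% and phi 0.3 the values are 0.007 and 0.017.

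**Power, and chance that only one test rejects**

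| IVIg vs SCIg | phi | Fisher power | Exact McNemar power | Opposite verdicts |
|---|---|---|---|---|
| 30% vs 60% | 0 | 0.51 | 0.45 | 8% |
| 30% vs 60% | 0.3 | 0.50 | 0.59 | 11% |
| 30% vs 60% | 0.5 | 0.49 | 0.77 | 27% |
| 5% vs 20% | 0.2 | 0.170 | 0.170 | 2.5% |
| 4% vs 12% | 0.2 | 0.025 | 0.024 | 0.3% |

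**Two single tables** (both, IVIg only, SCIg only, neither)

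- 7, 1, 8, 9, that is 8/25 vs 15/25, phi 0.39. Exact McNemar: b+c = 9, p = 2(1+9)/512 = 0.039. Fisher: p = 0.088.
- 4, 4, 12, 5, that is 8/25 vs 16/25, phi -0.20. Exact McNemar: b+c = 16, p = 2(1+16+120+560+1820)/65536 = 0.077. Fisher: p = 0.0465.

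The verdict can therefore flip in either direction.

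**The case against.** The strongest reply is that little changes in practice. Fisher's error rate passes 5% only for fairly common events with clearly negative correlation, and nothing in the SAP suggests that. At 20% in both phases the most negative correlation possible is -0.25, and Fisher's size there is 0.040. At 40% with correlation -0.1 it is 0.038. At 10% in both phases and correlation 0.3 the two tests have almost the same size (0.0020 and 0.0022). The large disagreement figures come from an event as common as 30% vs 60%; at 10% vs 20% and correlation 0.2, disagreement is 1.9%. This stands. It limits the weight of the point but does not make Fisher's test suitable for paired data.

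Second, the two sections do not test one identical endpoint. That also stands: the conflict is between methods for closely related comparisons. The misuse of Fisher's test in Section 5 is an error whatever Section 3 says.

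Third, some safety patients may lack an SCIg phase. "All patients enrolled at baseline constitute the safety population", whereas the intent-to-treat set in Section 5 needs at least one SCIg dose. If baseline means Week 0, as in Section 3's "from baseline (Week 0) to Week 12", few should be left out; otherwise more could be. Either way these are incomplete pairs, not an independent group.

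Fourth, Section 3 also names a one-sample test for a difference in proportions for treatment-related severity rates, which changing Fisher's test does not settle. This is correct and worth clearing up in the same edit.

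**Conclusion.** The concern holds. Section 5 puts a test for independent samples on paired data, and Section 3 uses a paired test for the same two phases. Nothing else in the SAP cures this.

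Fisher's test is too conservative under positive within-patient correlation and can exceed 5% only when the correlation is clearly negative. The argument for change is validity and consistency, not power: at zero correlation Fisher has slightly more power. The effect matters for common events and is small for uncommon ones. These sizes rest on assumed rates and correlations, two-sided testing and 25 complete pairs; that the test is wrong for the design does not. Because only secondary safety testing is affected, this is a change that should be made rather than a threat to the trial's main conclusion.

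**What to change.** In Section 5:

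- Replace treatment group(s) with study phase (IVIg, SCIg).
- Replace Fisher's exact test with McNemar's test for each adverse event, and again for the repeat without mild events.
- Use patients observed in both phases, and tabulate any others descriptively.
- Name one version of McNemar's test before analysis and use the same one in Section 3. The exact version keeps each single comparison at or below 5%; it does not adjust for testing many events.
- State which outcomes Section 3's one-sample test for severity rates covers, so that it does not overlap with McNemar's test.

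Fisher's test for prednisone increase against improvement in Section 3 can stay, because each patient appears in that table once.

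**Cost.** SAP wording only. Exact McNemar gives up a little power at zero correlation (0.45 vs 0.51 at 30% vs 60%) and gains nothing for uncommon events. The mid-p version is an option with more power, but it does not guarantee 5%: its largest size is 0.0498 at 25 pairs and 0.064 at 24, the latter only when nearly all pairs are discordant. Neither test adjusts for the unequal epochs (10 weeks of IVIg against 12 of SCIg), which should be noted when the results are reported.
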